Trial participants	Parents of children aged 0 to 2 months at baseline, identified by children's centre staff, self-referral, Health Visitors and parent advisory committee. Level of need is assessed by completion of a self-report mental health questionnaire (parent) and a parent-report measure of child social and emotional development. Co-parents are included in measure completion (and in parent programmes if parent is allocated to intervention condition at each level of intervention dose).
Sample size	606 participants allocated in a ratio of 5:1 (intervention:control)

Follow-up	Measures are administered during home or community based visits at four intervals; baseline and three follow-ups (2, 9 and 18 months post baseline assessment).
Primary analysis	Repeated measures analysis on ASQ:SE-2 scores, comparing treatment and control groups to investigate the effectiveness of the proportionate delivery of the IY E-SEE steps/model overall on child social and emotional wellbeing.
Key Secondary analyses	Repeated measures analysis on PHQ-9 scores, comparing treatment and control groups to investigate the effectiveness of the proportionate delivery of the IY E-SEE steps/model overall on parent depression levels

1 Introduction

This document outlines the detailed statistical analysis plan (SAP) for the E-SEE main trial and is intended to be read in conjunction with the current study protocol (v10. This SAP is written in conjunction with the International Conference on Harmonisation topic E9 (ICH E9 Expert Working Group, 1999), guidance for the content of SAPs in clinical trials (Gamble *et al.*, 2017), applicable statistical standard operating procedures (SOPs) from the University of Sheffield Clinical Trials Research Unit (CTRU) and trial documents (Protocol and Data Validation Specification). The trial is conducted in accordance with Good Clinical Practice in Clinical Trials (ICH Harmonised Tripartite Guideline, 1996) and Medicine for Human Use (Clinical Trials) Regulations (UK Statutory Instruments, 2004).

This SAP will guide the Trial Statistician during the statistical analysis of all quantitative outcomes in order to answer the objectives of the study. It excludes the health economic and process evaluations (which will be described elsewhere).

All analysis will be performed in a validated statistical software package such as R (Team, 2012).

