4.2 Inclusion in the Intervention arm

If a participant is allocated to the intervention arm, they receive the IY-I Book. Following the first follow up (2 months post baseline), only participants with a Parent PHQ-9 score ≥ 5 OR Child ASQ:SE2 score \geq 'Monitoring' in the intervention arm are offered the IY-I programme. Following the second follow up (9 months post baseline) only participants with Parent PHQ-9

³ In protocol v10 the CARE Index is described as a child attachment measure and listed as a child secondary outcome. Child attachment is just one part of the Index and we will use the overall dyadic synchrony score which is a parent-child dyad measure.

score ≥ 5 OR Child ASQ:SE2 score \geq 'Monitoring' in the intervention arm are offered the IY-T programme.

Non-research participants may be included in the IY-I and IY-T groups. Parents can be invited by service staff to join the group based on professional judgement/assessment that they meet the same eligibility criteria as research participants. We do not collect data for these participants; they attend as they would for any other parenting intervention delivered at that site. This is accepted practice in these types of research interventions when there are concerns about group size.

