7.7 Analysis of key secondary outcomes

The impact of the intervention on PHQ scores will be investigated using the same approach as the primary analysis of the primary outcome. Descriptive statistics will be presented for PHQ-9 at each time point (Appendix Table 6). Mean PHQ-9 scores and 95% CIs by treatment arm will be presented in line plots. Spaghetti plots will also be used to visualise individual changes over time.

The IY intervention in this trial comprises three main components – the IY-I book, IY-I and IY-T programmes. All participants who meet the eligibility requirement for being stepped up to IY-I and/or IY-T are given the opportunity to do so and there is no randomisation element in the step up. As such the following secondary analysis provides a non-randomised indicative analysis of the possible impact of individual components. The impact of individual components will be investigated using ASQ:SE-2 and PHQ-9 at the relevant follow up point with those participants in the control arm who would have been eligible for IY-I or IY-T in each case used as the control group comparator.

- Comparison between intervention and control groups at FU1 will provide an indicative analysis of IY-B;
- Comparison between intervention and control for the subgroup of parents with PHQ-9 score ≥ 5 OR Child ASQ:SE-2 score \geq Monitoring Zone at FU2 will provide an indicative analysis of IY-I;
- Comparison between intervention and control in the subgroup of parents with PHQ-9 score ≥ 5 OR Child ASQ:SE-2 score \geq Monitoring Zone at FU3 will provide an indicative analysis of IY-T.

These analyses will be conducted using multiple linear regression models including the same stratification variables (baseline ASQ:SE-2 score, baseline PHQ-9 score, sex of child and recruitment site) and potential confounders (ethnicity of the primary caregiver, marital status and highest level of education) as covariates. The mean difference, 95% confidence interval and associated p-values will be presented (Appendix Table 7).

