7.10 Changes from analysis specified in the Protocol

Section 10 of protocol version 10 says “Evaluating the overall effectiveness of the proportionate delivery of IY will be assessed using a multilevel mixed model to allow for a treatment and time effect whilst allowing for the clustering by participant and group treatments and confounding and stratifying variables”. As discussed in section 7.6.1 we will no longer account for treatment level clustering and will account for repeated measurements using a marginal model fitted using GEE.

Section 10 of protocol version 10 says “ITT analysis will be conducted at the cluster level using summary measures” as well as “the individual level with test statistics adjusted for intra-cluster correlation”. Because participants can get IY-I alone, IY-T alone or both, there is no way of grouping participants into clusters that remain stable throughout the intervention.

Sex of primary caregiver will no longer be used as a covariate due to the finding from the pilot that there were too few male primary caregivers for the associated model parameter to be estimated.

Section 10 of protocol version 10 says the ITT analysis will include “predictors of missing values”. This has been operationalised in this SAP by undertaking sensitivity analysis of the primary ITT using multiple imputation as described in section 8.1.1.

8 Detailed Statistical Methods and Calculations

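### The FU3 comparison labelled as IY-T also carries any lasting effect of the book and of earlier IY-I, so it is a cumulative contrast and not the impact of IY-T

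*SAP*

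**What the plan says.** Section 4.2 of the SAP gives every intervention family the book. It then applies the same need rule (PHQ-9 of 5 or more, or ASQ:SE-2 at or above Monitoring) twice. IY-I is offered after FU1: "Following the first follow up (2 months post baseline), only participants with a Parent PHQ-9 score" or child score at the threshold. IY-T is offered after FU2: "Following the second follow up (9 months post baseline) only participants with Parent PHQ-9" or child score at the threshold. Earlier IY-I does not exclude a family from IY-T, and section 7.10 confirms the overlap: "Because participants can get IY-I alone, IY-T alone or both".

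Section 7.7 sets out three component comparisons and introduces them with a caveat: "As such the following secondary analysis provides a non-randomised indicative analysis of the possible impact of individual components". The third, in the need-defined subgroup, "at FU3 will provide an indicative analysis of IY-T". The comparators are "those participants in the control arm who would have been eligible for IY-I or IY-T in each case used as the control group comparator". The regression includes "baseline ASQ:SE-2 score, baseline PHQ-9 score, sex of child and recruitment site", together with ethnicity, marital status and education. It has no FU1 or FU2 score and no term for earlier IY-I eligibility, offer or attendance. Table 7 has one FU3 row per outcome.

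**The concern.** The row is presented as information on one component, but its two sides differ by more than that component. The intervention side mixes families eligible at FU1, who had been offered IY-I, with families not eligible at FU1, who had not; all were allocated the book. The control side had services as usual throughout. Whatever lasts from the book and from IY-I therefore enters the difference at FU3.

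There is also a selection effect. If IY-I lowers scores, fewer IY-I families remain above the FU2 threshold, so the FU2-eligible groups in the two arms have different FU1 histories. Baseline adjustment does not restore the balance.

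This is distinct from the question of which visit defines the subgroup; it arises whether the threshold is read at FU2 or at FU3. What is at stake is the reading of the row. If IY-I works and lasts while IY-T adds nothing, the table would still tend to show a benefit under the IY-T label, with a confidence interval and p-value.

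**Working it through.** The SAP gives no figure for this comparison, so its size has to be simulated from Appendix B.

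**Check of the borrowed inputs.** Appendix B states an overall effect of 3.46, from 2.5 at FU1 and 15 for those stepped up at FU2. Its 13 cluster sizes sum to 76. From "606 participants allocated in a ratio of 5:1 (intervention:control"), the arms are 606 × 5/6 = 505 and 606/6 = 101. If 15 replaces 2.5 for the 76 stepped up:

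(2.5 + [2.5 × 429/505 + 15 × 76/505]) / 2 = (2.5 + 4.38) / 2 = 3.44

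This is close to 3.46. The denominator of 505 is an assumption. Other readings give 2.38 (effect at FU2 only in those stepped up) or 3.63 (15 added to 2.5).

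**Simulation inputs.**
- From the SAP: 5:1 allocation; SD 10 and correlation 0.4, i.e. a shared individual component with variance 40 plus error variance 60; means 26 (FU1) and 36 (FU2); Monitoring cut-offs 30, 40 and 50 for the 6-, 12- and 18-month versions.
- Assumed: baseline mean 20, FU3 mean 46, eligibility on ASQ:SE-2 alone, no book effect, true IY-T effect 0.
- IY-I effect: subtracted at FU2 from FU1-eligible intervention families who take it up; the maintained fraction is subtracted at FU3.
- Model: FU3 score regressed on arm and baseline score within the subgroup, 3 million families per scenario.

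**Uptake.** The share eligible at FU1 is P(Z ≥ (30 − 26)/10) = 0.345, and 0.345 × 505 ≈ 174. Appendix B's 76 stepped up gives 76/174 = 44%. Which programme the 76 describe is unclear, so full uptake and 44% at random are both shown.

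| IY-I effect, fraction kept at FU3 | Eligible at FU2, full uptake | Eligible at FU2, 44% uptake | Threshold at FU3, full uptake |
|---|---|---|---|
| 7.5, half | -1.5 | -0.6 | -0.7 |
| 7.5, all | -2.7 | -0.9 | -1.0 |
| 15, quarter | -1.5 | -0.4 | -0.7 |
| 15, half | -1.9 | -0.5 | -1.0 |
| 15, all | -2.8 | -0.8 | -1.0 |

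With the threshold at FU3 and 44% uptake the range is about -0.3 to -0.4.

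**Fading.** With eligibility at FU2 and full uptake, an IY-I effect of 5 gives -2.1 if fully kept and about -0.1 if it fades completely by FU3. An effect of 15 that fades completely still gives about -1.1, purely because IY-I changed who remained eligible at FU2.

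**Selection.** FU1-eligible families make up 51% of FU2-eligible controls, but under full uptake only 31% (effect 7.5) or 11% (effect 15) of FU2-eligible intervention families.

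**Split by FU1 eligibility.** Among families eligible at FU2 but not at FU1, the estimate is within about 0.1 of zero in every scenario above. With a lasting book effect of 2.5 (Appendix B's FU1 value) it is about -1.7. Among families eligible at both visits, 7.5 half kept and 15 a quarter kept both leave a residual effect of 3.75, yet the estimates are -2.5 and -1.0. That row is distorted by selection at FU2.

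**Covariates instead of a split.** Adding FU1 score, FU2 score and FU1 eligibility to the pooled model leaves about -1.9 to -2.2 for a lasting IY-I effect of 5 (correlation 0.4 and 0.7).

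**Precision of the IY-I-free row.** Assume the same eligibility rate at FU1 and FU2, and correlation 0.4. At 15%, P(both) = 0.049, leaving (0.150 − 0.049) × 101 ≈ 10 controls. At 50%, P(both) = 0.25 + arcsin(0.4)/2π = 0.315, leaving (0.500 − 0.315) × 101 ≈ 19. The residual SD is 10 × √(1 − 0.16) ≈ 9.2. The 95% half-width is 1.96 × 9.2 × √(1.2/n): 6.2 points for n = 10 and 4.5 for n = 19, before attrition.

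**The case against.** The SAP does not oversell this analysis. It says that step-up is not randomised, calls the result indicative, and states in Appendix B that the primary aim is the intervention as a whole. The larger figures need full uptake and eligibility at FU2, whereas 7.7 and Table 7, read literally, put the threshold at FU3; either change reduces the apparent effect substantially. Only part of a lasting IY-I effect transfers (about 40–60% for effects of 2.5 to 5). The proposed split is imprecise and not free of bias.

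Most of this stands, and it limits the size of the point and the claims made for the fix. The caveat does not dispose of the point, because it concerns the lack of randomisation and neither names nor handles carry-over. When earlier effects last, the direction is predictable and favours IY-T.

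A reader might infer that the row simply measures IY-I, that any benefit in it would be spurious, or that -1.5 to -2.8 is the bias to expect. The documents support none of these. They say nothing about how long IY-I effects last, Appendix B's own count suggests partial uptake, and a real IY-T effect would also appear in the row. Nor does the point touch the primary analysis, which estimates the whole programme.

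**Conclusion.** The label is wrong for what is estimated. The FU3 row contrasts the accumulated offer of book, IY-I for some, and IY-T with services as usual, in a need-selected subgroup. If earlier steps have lasting effects, part of them is credited to IY-T.

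For IY-I effects of 7.5 to 15 points, at least partly maintained, the misattributed amount is about -1.5 to -2.8 points (eligibility at FU2, full uptake), -0.4 to -1.0 (44% uptake), or -0.7 to -1.0 (threshold at FU3, full uptake). It is near 0 for an effect of 5 that has faded by FU3. These figures assume ASQ:SE-2 eligibility only and no book effect; a lasting book effect adds to them. They illustrate the mechanism and do not predict the trial's result.

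It is also tempting to treat the families eligible at FU2 but not FU1 as a clean test of IY-T. They are free of IY-I but not of the book. For a secondary analysis already described as indicative, relabelling is worthwhile and the split is a useful addition.

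**What to change.** In section 7.7 and Table 7:

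1. Label the pooled FU3 estimate as the cumulative effect of book, IY-I and IY-T in IY-T-eligible families, and do not call it the impact of IY-T.
2. Split it by eligibility at FU1, defined identically in both arms. Table 1 shows PHQ-9 and ASQ:SE-2 collected at FU1, so no new data are needed.
   - (a) Eligible at FU2 but not at FU1: report as the indicative IY-T comparison, free of IY-I but including any lasting book effect.
   - (b) Eligible at both: report as cumulative, and flag that it is selected on FU2 scores that IY-I may have changed.
3. Present row (a) as exploratory, with its interval.

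The cost is SAP wording and one or two extra rows per outcome. The downside is imprecision in row (a): about 10 to 19 controls before attrition if 15–50% of about 101 are eligible at FU2, and a 95% half-width of about 4.5 to 6 points, wider than the carry-over it is meant to remove. The relabelling in step 1 has no such drawback and should be made even if the split is not adopted.

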7.8 Analysis of other secondary outcomes

Not all secondary outcomes will be collected at all four time points. For those outcomes that have been collected at all four time points (PSoC, EQ5D-5L, CARE Index), mean scores by treatment arm will be presented in line plots (Figure 4) and the impact of the intervention on these outcomes will be investigated using the same approach as the primary analysis of the primary outcome.

For those outcomes only collected at FU3 (MPAS/PPAS, PEDSQL, SDQ), descriptive statistics will be presented by treatment arm. A multiple linear regression model will be used to estimate the adjusted mean difference between treatment arms. Stratification variables (baseline PHQ-9 score, baseline ASQ:SE-2 score, sex of child and site) will be included in the model as covariates.

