7.1 General Considerations

Data will be reported according to the Consolidated Standards Of Reporting Trials (CONSORT) statement for individually randomised parallel group trials (Schulz, Altman and Moher, 2010) and extension (Juszczak *et al.*, 2019).

Summaries of continuous variables will comprise the number of observations used, mean, median, standard deviation (SD), inter-quartile range (IQR), minimum and maximum as appropriate for the distribution of the data.

Summaries of categorical variables will comprise the number of observations used, and the number and percentage of observations in each category. Tables containing the results of the statistical modelling will present the overall difference between treatment groups with two-sided 95% confidence intervals (CI) and p-values. Hypothesis tests will use a two-sided 5% significance level.

Complete details of data derivations and methods for handling missing data is covered in sections 8.1 and 9.

All analyses are based on the overall score only unless otherwise stated.

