7.6 Analysis of the primary outcome

7.6.1 Primary Analysis of the primary outcome

The ASQ:SE-2 is a set of questionnaires with different versions for different age groups. Consequently, different versions will be completed at each time point. The primary analysis will use raw ASQ:SE-2 scores as the scoring is the same across treatment arms and estimates will be easier to interpret. For ASQ:SE-2 either the 2 month or the 6 month questionnaire is administered at Follow-up 1 dependent upon the developmental age of the baby. If we observe an imbalance between arms in the number receiving the 2 months and 6 months versions we will adjust the score for those receiving the 2 months version by multiplying by 1.24. We have based the adjustment on the monitoring thresholds (25 and 30 for the 2 and 6 months surveys) and referral thresholds (35 and 45 for the 2 and 6 months surveys). The adjustment is midway between those required to preserve the monitoring threshold (30/25) and the referral threshold (45/35). If participants have completed both questionnaires, we will use the 6 months version and exclude them from the potential adjustment procedure.

The overall treatment effect will be estimated using a marginal model fitted using general estimating equations to account for the repeated measures with a Gaussian family, identity link, robust standard errors and an autoregressive covariance structure of order 1 AR(1). If the model does not converge using AR (1) we will use an unstructured correlation structure. The fixed effects will be stratifying variables (baseline ASQ:SE-2 score, baseline PHQ-9 score,

site⁴ and sex of child); potential confounders (ethnicity of the primary caregiver, marital status and highest level of education and follow up time (using an indicator variable for each time point)).

- The therapist induced clustering effect will not be fitted because the offer of IY-I and IY-T is conditional on outcome at FU1 and FU2 so clustering is confounded with treatment effect leading to biased estimation of the latter.
- The repeated measurements will be accounted for using a marginal model fitted using GEE because accounting for repeated measures using a mixed model inflates the type 1 error (random intercept only model) or gives a biased estimate of the treatment effect (random intercept and slope model).

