This table will be repeated for Primary caregiver and co-parent PHQ-9 scores

[figure not shown]

Figure 2: Forest plot showing results from the primary analysis

[figure not shown]

Figure 3: Line plot of mean ASQ:SE-2 at each time point
This figure will be repeated for PHQ-9

Table 7: Results of the analysis of key secondary outcome 2

Outcome measure	n	Mean (SD) Intervention	n	Mean (SD) Control	n	Mean difference (95%CI)	Adjusted Mean difference (95%CI)*	p-value
ASQ:SE-2 at FU1	xx	xx.x(xx.x)	xx	xx.x(xx.x)	xx	xx.x(xx.x-xx.x)	xx.x(xx.x-xx.x)	0.xxxx
ASQ:SE-2 at FU2 in the subgroup of parents with PHQ-9 score >=5 OR Child ASQ:SE2 score>= Monitoring Zone	Xx	xx.x(xx.x)	xx	xx.x(xx.x)	xx	xx.x(xx.x-xx.x)	xx.x(xx.x-xx.x)	0.xxxx
ASQ:SE-2 at FU3 in the subgroup of parents with PHQ-9 score >=5 OR Child ASQ:SE2 score>= Monitoring Zone	xx	xx.x(xx.x)	xx	xx.x(xx.x)	xx	xx.x(xx.x-xx.x)	xx.x(xx.x-xx.x)	0.xxxx

This table will be repeated for primary care givers and co-parents (PHQ-9 scores)

iv. Analysis of secondary outcomes results

Table 8 : EQ5D-5L for primary care-givers

	n	Mean (SD) Intervention	n	Mean (SD) Control	n	Mean difference (95%CI)	Adjusted Mean difference (95%CI)*	p-value
Primary carer EQ5D-5L								
Baseline	xx	xx.x(xx.x)	xx	xx.x(xx.x)	xx	xx.x(xx.x-xx.x)		
FU1	xx	xx.x(xx.x)	xx	xx.x(xx.x)	xx	xx.x(xx.x-xx.x)	xx.x(xx.x-xx.x)	0.xxxx
FU2	xx	xx.x(xx.x)	xx	xx.x(xx.x)	xx	xx.x(xx.x-xx.x)	xx.x(xx.x-xx.x)	0.xxxx
FU3	xx	xx.x(xx.x)	xx	xx.x(xx.x)	xx	xx.x(xx.x-xx.x)	xx.x(xx.x-xx.x)	0.xxxx

*adjusted for baseline ASQ:SE-2 score, baseline PHQ-9 score, sex of child and recruitment site and baseline measure
 This table will be repeated for secondary outcome data collected at FU2 and FU2

Each Secondary outcomes will be reported in separate table showing outcome by time-point in a similar manner to table

[figure not shown]

Figure 4: Line plot showing mean secondary outcome scores

v. Subgroup analysis results

Table 9: Results of subgroup analysis

Subgroup	n	Mean (SD) Intervention	n	Mean (SD) Control	n	Mean difference (95%CI)*	p-value*
TBC	xx	xx.x(xx.x)	xx	xx.x(xx.x)	xx	xx.x(xx.x-xx.x)	0.xxxx
	xx	xx.x(xx.x)	xx	xx.x(xx.x)	xx	xx.x(xx.x-xx.x)	
	xx	xx.x(xx.x)	xx	xx.x(xx.x)	xx	xx.x(xx.x-xx.x)	
	xx	xx.x(xx.x)	xx	xx.x(xx.x)	xx	xx.x(xx.x-xx.x)	0.xxxx
	xx	xx.x(xx.x)	xx	xx.x(xx.x)	xx	xx.x(xx.x-xx.x)	
	xx	xx.x(xx.x)	xx	xx.x(xx.x)	xx	xx.x(xx.x-xx.x)	0.xxxx
	xx	xx.x(xx.x)	xx	xx.x(xx.x)	xx	xx.x(xx.x-xx.x)	
	xx	xx.x(xx.x)	xx	xx.x(xx.x)	xx	xx.x(xx.x-xx.x)	

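### Section 7.8 and Table 8 specify different models for PSoC, EQ-5D-5L and CARE-Index, and 7.8 read literally leaves out the outcome's own baseline and so loses some precision

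*SAP*

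**What the plan says.** SAP section 7.8 takes the outcomes measured at every visit ("For those outcomes that have been collected at all four time points (PSoC, EQ5D-5L, CARE Index") and says that "the impact of the intervention on these outcomes will be investigated using the same approach as the primary analysis of the primary outcome".

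That approach is set out in 7.6.1: a GEE model giving one overall treatment effect. On covariates it reads "The fixed effects will be stratifying variables (baseline ASQ:SE-2 score, baseline PHQ-9 score", then site and sex of child, followed by "potential confounders (ethnicity of the primary caregiver, marital status and highest level of education and follow up time (using an indicator variable for each time" (one indicator per follow-up). No treatment-by-time term is stated.

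Appendix A, Table 8 is the results shell for primary-caregiver EQ-5D-5L. Its adjusted column is footnoted "adjusted for baseline ASQ:SE-2 score, baseline PHQ-9 score, sex of child and recruitment site and baseline measure". It has adjusted differences and p-values at FU1, FU2 and FU3, and no overall row. A note below it extends the layout: "Each Secondary outcomes will be reported in separate table showing outcome by time-point in a similar manner to table".

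Section 7.1 says that tables of modelling results give the overall difference between arms. Section 7.10, on departures from the protocol, does not mention the two covariate lists.

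**The concern.** In 7.6.1 the baselines of ASQ:SE-2 and PHQ-9 are in the model as named stratifying variables. The primary and key secondary outcomes are therefore adjusted for their own baseline automatically. When 7.8 carries the model over to PSoC, EQ-5D-5L and CARE-Index, the list carried over has no such term for them. The only place that supplies it is a dummy-table footnote, and that footnote drops three covariates that the text includes.

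Two statisticians following this SAP could therefore fit different models to the same outcome. Omitting a baseline value that is already in hand widens the confidence interval and gains nothing. An unsettled covariate list also leaves a choice open after the statistician receives unblinded data at database freeze (4.3).

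**Working it through.** **Step 1: the two specifications side by side.**

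| Element | 7.8 via 7.6.1 | Table 8 and footnote |
|---|---|---|
| Baseline ASQ:SE-2, baseline PHQ-9 | yes | yes |
| Site, sex of child | yes | yes |
| Ethnicity, marital status, education | yes | no |
| Outcome's own baseline | not listed | yes |
| Treatment effect | one overall | one per follow-up |

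The lists differ in both directions. The footnote's list is the stratifier-only set that 7.8 gives for outcomes measured at FU3 alone, plus the baseline measure. Table 1 (section 6.1) confirms that PSoC, EQ-5D-5L and CARE-Index are all collected at baseline. With no treatment-by-time term, the 7.6.1 model as stated cannot fill the three visit rows of Table 8.

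**Step 2: what omitting the own baseline costs.** The SAP gives no standard error, power or correlation for these outcomes, so there is no stated figure to reproduce. The only between-visit correlation in the SAP is 0.4 in Appendix B. That is a simulation assumption for a scenario modelled on the primary outcome, with equal correlation between time points. I therefore assume r from 0.3 to 0.6 under two structures.

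The overall effect is approximated by the mean of the three follow-ups, with unit SD. Let V be the variance of that mean and C its covariance with baseline.

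- Exchangeable: V = (1 + 2r)/3 and C = r.
- AR(1), equal steps: V = (3 + 4r + 2r²)/9 and C = (r + r² + r³)/3.

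The residual variance is V without the own baseline and V − C² with it. The SE ratio is √[V/(V − C²)]. Sample size and allocation ratio cancel.

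The last column supposes that a baseline covariate already in the model (such as PHQ-9) correlates c = 0.5 with the own baseline and relates to follow-up only through it. The ratio is then √[(V − c²C²)/(V − C²)].

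| Structure | r | V | C² | V − C² | SE ratio | SE ratio, c = 0.5 |
|---|---|---|---|---|---|---|
| Exchangeable | 0.3 | 0.533 | 0.090 | 0.443 | 1.097 | 1.073 |
| Exchangeable | 0.4 | 0.600 | 0.160 | 0.440 | 1.168 | 1.128 |
| Exchangeable | 0.5 | 0.667 | 0.250 | 0.417 | 1.265 | 1.204 |
| Exchangeable | 0.6 | 0.733 | 0.360 | 0.373 | 1.402 | 1.313 |
| AR(1) | 0.3 | 0.487 | 0.019 | 0.467 | 1.020 | 1.015 |
| AR(1) | 0.4 | 0.547 | 0.043 | 0.503 | 1.042 | 1.032 |
| AR(1) | 0.5 | 0.611 | 0.085 | 0.526 | 1.078 | 1.059 |
| AR(1) | 0.6 | 0.680 | 0.154 | 0.526 | 1.137 | 1.104 |

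Example at r = 0.4: exchangeable, 0.600/0.440 = 1.364, square root 1.168; AR(1), 0.547/0.503 = 1.086, square root 1.042.

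**The case against.** The strongest reply is that 7.8 refers to the same approach, not the same covariates. The primary model adjusts for the baseline of its own outcome, and so does the PHQ-9 model in 7.7. A sensible statistician would do likewise for PSoC, EQ-5D-5L and CARE-Index, the footnote says so, and nothing in the SAP excludes it. This partly stands: it is a fair guess at the intention. But 7.6.1 labels those baselines as stratifying variables, not as the outcome's baseline, and the footnote that would confirm the intention disagrees with the text on three other covariates. The model remains unspecified.

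The reply on size also stands. A reader might take the Appendix B value of 0.4 with equal correlation and conclude that the plan costs 17% in standard error, or 36% in variance. The documents do not support that as an estimate: the 0.4 was not put forward for these outcomes, the planned working structure is AR(1), and EQ-5D-5L contains an anxiety/depression item that is likely to overlap with PHQ-9. Under equal-step AR(1) the same 0.4 gives about 4%.

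A reader might also infer that Table 8 licenses three tests per outcome. Under the rule in 7.1 ("Hypothesis tests will use a two-sided 5% significance level") that would put the chance of a false positive anywhere from 0.05 to 1 − 0.95³ = 0.143, the upper end if the tests were independent. The documents do not support this reading either. Sections 7.1 and 7.6.1 point to a single overall difference, and Table 8 is an unfinished shell, with FU2 named twice and a table reference left without its number. The shell should be brought into line with the text, but it does not override it.

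**Conclusion.** The inconsistency is real and rests on the text alone. Section 7.8, through 7.6.1, and the Table 8 footnote give different covariate lists for the same outcomes, Table 8 lacks the overall difference that 7.1 requires, and 7.10 reconciles neither.

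If 7.8 is followed literally, the cost is precision only, because randomisation keeps the treatment estimate unbiased with or without the own baseline. For r of 0.3 to 0.6 the standard error is larger by about 2% to 14% under equal-step AR(1), or 10% to 40% under exchangeable correlation. With an overlapping covariate at c = 0.5 the ranges become about 2% to 10% and 7% to 31%. These figures rest on assumed correlations, on equal spacing although follow-ups fall at 2, 9 and 18 months, and on an equally weighted mean of the three visits.

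The outcomes are secondary and the primary result is untouched. The correction is still worth making before database freeze, because it costs nothing and settles the model in advance.

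**What to change.** - In 7.8, state that PSoC, EQ-5D-5L and CARE-Index are analysed with the primary GEE model plus the baseline value of the outcome being analysed.
- Give the same full covariate list in the Table 8 footnote: the 7.6.1 list, including ethnicity, marital status and education, plus the own baseline.
- Add the overall GEE difference, with its confidence interval and p-value, as the inferential row of Table 8. Keep the FU1, FU2 and FU3 figures as descriptive.

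The cost is one sentence, one footnote and one table row. The baseline data are already collected, and no other analysis changes.
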